**Co-Investigator: [name] M.D. [[contact]](mailto:[contact])**

**Co-Investigator: [name]. [[contact]](mailto:[contact])**

**Protocol version: 3.0**

**Protocol date: 05/25/2016**

**Study site(s): Cleveland Clinic**

**CCF IRB #: 16-960**

**Approval Date: 08/22/2016**

**Expiration Date: 08/04/2017**

**Background:** The gold standard to diagnose cardiac involvement in amyloidosis is endomyocardial biopsy. Non-invasive diagnostic modalities have become more commonplace in the recent past. Echocardiography with strain imaging, cardiac MRI and technetium-99m pyrophosphate (TcPYP) nuclear SPECT scintigraphy are often used. TcPYP is a bone radiotracer that binds to calcium in amyloid fibrils and demonstrates myocardial uptake in cases of TTR amyloidosis only. This tracer is FDA approved for imaging in cardiac amyloidosis, yet it is a non-specific tracer with unclear sensitivity and specificity in early disease. In addition, there is no current nuclear tracer that can be used for AL amyloidosis.

Florbetapir F-18 is a radiotracer approved by the FDA for the use in positron emission tomography (PET) imaging of cerebral amyloid deposits for Alzheimer diseases. With regard to cardiac disease, one small study has confirmed the uptake of Florbetapir in both ATTR and AL cardiac amyloidosis.[1] Similar to Alzheimer disease, we postulate that Florbetapir will show improved detection of cardiac amyloidosis over conventional non-invasive imaging techniques, particularly in early disease.

Our hypothesis is that F-18 florbetapir will detect amyloid deposition in myocardium prior to current non-invasive diagnostic measures, particularly echocardiography with strain and technetium pyrophosphate scintigraphy. We intend to use Florbetapir to assess the correlation between the standard TcPYP scintigraphy with this novel imaging modality. Additionally, we would like to examine the ability of florbetapir to detect early cardiac involvement by imaging patients with extra-cardiac biopsy proven TTR amyloidosis.

### Study Aim

- 1) To assess the role of Florbetapir in the early detection of cardiac amyloidosis.
- 2) To assess the correlation between TcPYP scintigraphy and F-18 florbetapir

### Significance of the Study

This tracer is currently used for the early detection of brain amyloid (Alzheimer's disease). Early detection of Alzheimer disease is paramount, as treatment options are most beneficial when diagnosed early. Several recent studies support early amyloid detection by brain PET imaging using Florbetapir. This concept parallels the significance of this tracer in cardiac amyloidosis. As novel therapies evolve for cardiac amyloidosis, early detection of end organ involvement is essential as treatment options are most beneficial when started early. In addition, a non-invasive sensitive tracer will allow for monitoring of disease progression with treatment and may be used as a surrogate endpoint in future studies.

This study will allow us to identify the sensitivity and specificity of this tracer and compare it to technetium pyrophosphate. In addition, we can subsequently follow patients who have uptake of florbetapir in the myocardium to see if they develop clinical events such as new heart failure or echocardiographic findings to suggest presence of cardiac disease.

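### The Significance section promises florbetapir's sensitivity and specificity, but the plan assigns no reference standard for cardiac involvement to the amyloid patients

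*Combined protocol and SAP*

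**What the plan says.** Significance of the Study states: "This study will allow us to identify the sensitivity and specificity of this tracer and compare it to technetium pyrophosphate". The Study Aim section sets two aims: "To assess the role of Florbetapir in the early detection of cardiac amyloidosis" and "To assess the correlation between TcPYP scintigraphy and F-18 florbetapir". Neither names sensitivity or specificity, and Data Analysis names no accuracy measure.

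The rest of the plan bears on cardiac status as follows.

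- **Background:** "The gold standard to diagnose cardiac involvement in amyloidosis is endomyocardial biopsy". TcPYP "demonstrates myocardial uptake in cases of TTR amyloidosis only", "yet it is a non-specific tracer with unclear sensitivity and specificity in early disease". The hypothesis is that florbetapir detects myocardial amyloid "prior to current non-invasive diagnostic measures, particularly echocardiography with strain and technetium pyrophosphate scintigraphy".
- **Methods:** amyloid patients enter on a biopsy from outside the heart and on free light chains. Echocardiographic evidence of cardiac amyloidosis with septal and posterior walls of at least 13 mm is an exclusion. Ten controls have a negative extra-cardiac biopsy. Imaging is by PET/MRI.
- **Data Analysis:** blinded readers grade 17 segments from 0 to 4 and record segmental uptake values. No rule turns these into a positive or negative patient.
- **Variables:** echocardiographic measures (including strain), laboratory values and PET scores are listed. Myocardial biopsy, MRI findings and the TcPYP result are not.
- **Follow-up:** Significance says "we can subsequently follow patients who have uptake of florbetapir in the myocardium" and names new heart failure and echocardiographic signs of cardiac disease as the events of interest. Methods refers back to this.

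**The concern.** Sensitivity is the proportion positive among patients with cardiac involvement; specificity is the proportion negative among those without. Both denominators require a reference standard applied to the people scanned. If none is assigned, any accuracy figure reported later would rest on a reference chosen without declaration, possibly after the images have been read.

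The choice would matter here. Were strain or TcPYP used as the reference, a patient with florbetapir uptake and a still-normal comparator would be scored as a false positive. That is exactly the finding the Background hypothesis looks for.

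**Working it through.** **1. The plan's own figure.** The sample size of 40 is set by the number of tracer doses supplied. No power or precision target stands behind it, so there is no accuracy calculation to reproduce. The plan does not say whether the 10 controls are among the 40, so the amyloid group is 30 or 40.

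**2. Each candidate reference, set against the plan.**

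| Candidate | Why it does not serve as specified |
|---|---|
| Endomyocardial biopsy | Named in the Background; neither required in Methods nor listed in Variables |
| Entry criteria | Establish amyloid outside the heart or abnormal light chains, not cardiac status |
| Wall thickness on echo | Overt cases are excluded, so they cannot supply known positives |
| TcPYP | The comparator; described as TTR-only and of unclear accuracy in early disease; not in Variables |
| Strain | A test florbetapir is hypothesised to precede |
| MRI | Part of the scan; given no reference role and no listed variable |
| Troponin T, NT-proBNP | Collected, but no definition of involvement is built from them |
| Follow-up | Described under Significance for patients with uptake; no duration or operational event criteria |

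**3. What the amyloid data alone can say.** With N patients, P positive on florbetapir and D truly involved but unidentified, the number of true positives lies between max(0, D + P − N) and min(D, P). Sensitivity is TP/D, and specificity is (N − D − (P − TP))/(N − D).

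- Assume N = 30, P = 12, D = 12. TP runs from 0 to 12, so sensitivity runs from 0/12 = 0% to 12/12 = 100%, and specificity from (18 − 12)/18 = 33% to 18/18 = 100%.
- Assume N = 40, P = 16, D = 16. The bounds are the same: 0% to 100%, and (24 − 16)/24 = 33% to 100%.
- Other assumed values can narrow the bounds. With N = 30, D = 24 and P = 18, TP runs from 12 to 18 and sensitivity from 50% to 75%. That narrowing comes only from treating D as known, which it is not.

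**4. Following only patients with uptake.** Assume N = 30, 12 positive, 10 of them later confirmed, and 18 negatives unverified. Sensitivity is 10/(10 + missed cases): 10/10 = 100% if none is missed, 10/28 = 36% if all 18 are. Only a positive predictive value, 10/12 = 83%, could be estimated.

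**5. The controls.** Suppose a positivity threshold has been set and a negative extra-cardiac biopsy is accepted as ruling out cardiac amyloid. Exact (Clopper-Pearson) 95% intervals for specificity are:

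- 10/10 negative: lower limit 0.025^(1/10) = 0.692, so 69% to 100%
- 9/10 negative: 55.5% to 99.7%
- 8/10 negative: 44% to 97%

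So even with no positive control, a false-positive rate of up to 1 − 0.692 = 30.8% is not excluded.

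**The case against.** The strongest reply is that the sentence is motivation. It sits under Significance, the aims do not mention accuracy, no accuracy analysis is planned, and this is a small study limited by tracer supply. Much of that stands. The aim of correlating florbetapir with TcPYP needs no reference standard. A reader might infer that the study cannot meet its aims; the documents do not support that. But the sentence says what the study will deliver, and on that it is wrong.

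Four further readings go too far.

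- **The plan names no gold standard.** It does, in the Background. What is missing is its assignment, or that of any substitute, to the participants.
- **Specificity is at least available from the controls.** Not yet: segment grades and uptake values do not define a positive patient, so a threshold must come first.
- **Follow-up is undefined.** The events are named; the duration and operational criteria are absent. The back-reference in Methods could be read as covering everyone scanned, but even then there is no verification as written.
- **A 30.8% limit means about 9 of 30 amyloid patients may be falsely positive.** The product 0.308 × 30 = 9.2 is a ceiling that assumes none of the 30 has cardiac involvement. If half did, it would be 0.308 × 15 = 4.6.

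**Conclusion.** The concern holds for the Significance sentence and should be corrected. As specified, neither sensitivity nor specificity can be estimated in the amyloid patients, whether they number 30 or 40. The most the design could yield is a crude specificity from 10 controls, with an exact 95% interval no better than 69% to 100%. That is conditional on a pre-set positivity threshold and on taking a negative extra-cardiac biopsy as excluding cardiac amyloid.

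The absence of an assigned reference is read directly from the documents. The ranges in steps 3 and 4 of the working use assumed counts and illustrate non-identifiability; they do not predict this study's results.

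**What to change.** Replace the sentence with: *This study will estimate the proportion of participants with myocardial florbetapir uptake and its agreement with TcPYP and with echocardiographic strain.* Make no sensitivity claim. To support the new sentence:

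1. Set the patient-level florbetapir positivity threshold and the cut-off for normal strain before images are read.
2. Report uptake proportions with exact 95% intervals in AL patients, ATTR patients and controls. Label the control figure a false-positive rate in biopsy-negative people.
3. Add the existing TcPYP result to the Variables list and state how many patients have one. Cross-tabulate uptake against TcPYP, separately for ATTR and AL.
4. Cross-tabulate uptake against strain. Describe uptake with normal strain as consistent with earlier detection, not as a test of it.
5. Do not present follow-up as verification unless it covers all scanned patients, with a stated duration and event criteria.

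The cost is one replaced sentence, two cut-offs, one added variable, a few descriptive tables and a clarified follow-up statement. No new scans are needed; extending follow-up to everyone would add some chart review. The downsides are a narrower stated conclusion and TcPYP agreement limited to patients who have that scan. False uptake and true early involvement will remain inseparable.

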## Methods

This is a prospective, study that will recruit patients at Cleveland Clinic.

Inclusion Criteria:

1. Patients with extra-cardiac biopsy proven AL or ATTR amyloidosis
2. Patients with a ratio of affected to unaffected free light chains >5 or free light chain difference of >50

Exclusion Criteria:

1. Echocardiographic evidence of cardiac amyloidosis with septal and posterior wall thickness  $\geq$  13mm
2. Contraindication to florbetapir or its components
3. Refusal to participate in the study

Control group:

1. We will also include 10 "control" patients without amyloidosis who had a negative extra-cardiac biopsy for amyloidosis.

Patients will undergo PET/MRI imaging with florbetapir. The result will be available clinically and released to the provider. Patients will be followed as above.

## Logistics:

- The amyloidosis clinical research fellow will screen patients and contact them, notifying them of the study
- HVI clinical research nurse will consent patient at the time of regularly scheduled outpatient visit or TcPYP scan
- Patient will be scheduled for F-18 florbetapir PET
- Patient will undergo F-18 florbetapir PET
  - Radiotracer will be supplied without cost from Avid pharmaceuticals
  - Siemens PETNET will process the tracer in the on-site cyclotron. This is already being done at Cleveland Clinic for brain imaging in Alzheimer's disease
- The study PI and co-investigator will interpret images

**Sample size:** We aim to enroll 40 patients, as Avid pharmaceuticals have agreed to provide us with 40 doses of florbetapir.

**Data Analysis:** Images will be interpreted by two experienced readers blinded to clinical data and TcPYP scintigraphy results. Image will be read with both semi-quantitative measures (17 segment model with uptake graded 0-4) and quantitatively (with segmental uptake values).

**Patient Risk:** There is risk carried by the radiation for the scan. Each F-18 florbetapir scan is dosed at 10mCi and estimated to deliver an equivalent dose of radiation of 7 mSv based on dosing for a 70kg person. Based upon the BEIR VII preferred model, overall cancer incidence given this amount of radiation per nuclear

scan for a 60 year old was calculated to be 0.034% for males and 0.062% for females. This was calculated using Table 12D-1 from the BEIR VII report (see appendix) which reports the incidence of cancer cases based upon 100mSv equivalent doses per 100,000 persons exposed. The lifetime risk for cancer mortality is 0.022% for males and 0.029% for females per scan using Table 12D-2.

In addition, there is a risk of adverse reaction. In one trial, one patient with AL amyloidosis currently undergoing chemotherapy developed nausea during the scan. [1] There were no reported adverse events in the other study. [2] In the FDA approval of florbetapir, there were “no serious adverse reactions in the studies and the reported adverse reactions were predominantly mild to moderate in severity.”

**Variables:**

- Clinical variables will be collected including age, sex, race, BMI, hypertension, diabetes, hyperlipidemia, coronary artery disease
- Echocardiographic variables including LA/LV/RA/RV volumes, LV mass, anterior and posterior wall thickness, LVIDD, LVISD, EF, E velocity, A velocity, deceleration time, septal and lateral e', RVSP, valve lesion severity, RV s', RV FAC, LV and RV longitudinal strain
- Laboratory variables including CBC, CMP, troponin T and NT-proBNP
- Florbetapir-PET variables including segmental semiquantitative scores and SUVs

